## 9.0 STUDY PLAN

### 9.1 Study Procedures

#### 9.1.1 Informed Consent and HIPAA Release

Written informed consent will be obtained from each subject prior to performing any study-specific evaluations. The HIPAA release is embedded in the informed consent document. The informed consent document is subject to review and approval by the Sponsor and will be approved by a qualified IRB. The IRB-approved document must contain, at minimum, the eight basic elements of informed consent set forth in applicable law. Only the most recently IRB-approved informed consent document must be used to consent prospective study subjects. The Investigator (according to applicable regulatory requirements), or a person designated by the Investigator and under the Investigator's responsibility, will fully inform the potential study subject of all pertinent aspects of the Clinical Study, including written information given approval/favorable opinion by the IRB/IEC.

Prior to the potential subject's participation in the Clinical Study, the written informed consent form must be signed, name filled in and personally dated by the subject and by the person who conducted the informed consent discussion, and by the Investigator. One copy of the signed and dated informed consent document will be given to the subject and the original retained by the Investigator/site.

#### 9.1.2 Screening

Investigators must account for all subjects who sign informed consent forms. The Investigator will keep a Subject Screening and Enrollment Log at the investigational site. Subjects who have screen failed may be allowed to re-screen once at the discretion of the Investigator. A new screening number will be assigned.

Subjects who meet all of the inclusion criteria and none of the exclusion criteria are eligible for this study. If subjects are fasting (only water for  $\geq 10$  hours), all screening assessments may be done on the same day. If subjects are not fasting, they will be invited to return for a second screening visit to complete any missing screening procedures (e.g. laboratory assessments).

Subjects will be instructed on influencing factors and restrictions such as grapefruit containing food and beverages, star fruit (carambola), pomegranate, Seville orange and other food components that may interact with CYP3A4, smoking or medication and illness/infection.

If subjects don't have a diagnosis of NASH stage 2/3 assessed by liver biopsy performed within 24 months, FibroScan® (CAP) will be evaluated instead to identify subjects who are likely to have a liver fat content of  $\geq 10\%$  at MRI-PDFF. Depending on the outcome/results of these values, the subjects will proceed to MRI-PDFF or not. For further details on

parameters and outcome for the determination to proceed to MRI-PDFF see the Operations Manual.

Subjects MELD score will be calculated according to the following formula:

$$\text{MELD(i)} = 0.957 \times \ln(\text{Cr}) + 0.378 \times \ln(\text{bilirubin}) + 1.120 \times \ln(\text{INR}) + 0.643$$

Then, round to the tenth decimal place and multiply by 10. For further details see the Operations Manual.

### 9.1.3 Demographics and Medical History

Demographic information, medical history and prior medications will be obtained at Screening.

### 9.1.4 Physical Examination

The baseline physical examination (PE) will consist of the following body systems: (1) eyes; (2) ears, nose, throat, neck, thyroid; (3) cardiovascular system; (4) respiratory system; (5) gastrointestinal system, mouth; (6) dermatologic system, including hair; (7) extremities; (8) musculoskeletal system; (9) central and peripheral nervous system, (10) lymph nodes and (11) testicular examination in male subjects.

An abbreviated PE will be performed by the Investigator (or a qualified physician at the investigational site) at time points indicated in the SOE in section [16.1](#) for each cohort.

For abbreviated PEs, the following will be examined and/or measured by the Investigator or medically-qualified designee: skin (crust, erosion, ulcer, rash, inflammation, etc); eyes (dryness, conjunctivitis, etc); hair (assessment of male pattern baldness using the Norwood scale [see Appendix D in section [16.4](#)] or assessment of female pattern hair loss using the Savin scale [see Appendix E in section [16.5](#)]); lymph nodes; and respiratory, cardiovascular, abdominal (gastrointestinal), and musculoskeletal systems.

In addition, male subjects will undergo a testicular examination on C1/D-1 and C4/D29.

A complete physical examination may be performed in case the subjects have symptoms or at the discretion of the Investigator.

### 9.1.5 Height, Weight, and BMI

Height (without shoes) will be measured once, during the Screening visit

Weight (without shoes) will be measured fasting in the morning, with light clothing and post void at time points indicated in the SOE in section [16.1](#).

BMI ( $\text{kg}/\text{m}^2$ ) will be calculated from height and weight.

### 9.1.6 Vital Signs

Vital signs will include body temperature (aural), supine blood pressure (after 5 minutes resting), respiration rate and pulse rate (after 5 minutes resting). Vital sign measurements will be performed at days indicated in the SOE in section [16.1](#).

### 9.1.7 Concomitant Illness and Therapy

Concomitant therapy is any medication given in addition to the investigational product (including over-the-counter medications, herbal medications, and vitamin supplements) administered between screening and follow-up.

Concomitant illness is any significant medical condition or disease that is present at study start (signing of informed consent). This includes clinically significant laboratory, ECG, or physical examination abnormalities noted at Screening examination.

Details of all concomitant illnesses and therapies must be recorded at study entry and must be recorded on the subject's CRF. Any changes in concomitant medication must be recorded at each visit. If the change influences the subject's eligibility to continue in the study, the Sponsor must be informed. The information collected for each concomitant medication includes, at a minimum, start date, stop date or continuing, and indication.

AEs related to administration of these therapies or procedures must also be documented on the appropriate eCRF.

For prohibited medications, please see [Table 7-1](#) Prohibited Medication.

### 9.1.8 Procedures for Clinical Laboratory Samples

All samples will be collected in accordance with acceptable laboratory procedures. Laboratory samples will be taken as described in the SOE in section [16.1](#).

Additional samples (e.g., including blood samples, urine samples and all types of tissue samples) may be collected and stored for potential future analysis. For details please see the Laboratory Manual.

**Table 9-1 Clinical Laboratory Assessments**

Hematology	Serum Chemistry	Urinalysis
CBC with differential: Hematocrit Hemoglobin mean corpuscular volume (MCV) mean corpuscular hemoglobin (MCH) mean corpuscular hemoglobin concentration (MCHC) red cell distribution width (RDW)	Hepatic function panel: Alanine aminotransferase (ALT/SGPT) albumin, serum alkaline phosphatase, serum aspartate aminotransferase (AST/SGOT) bilirubin, direct bilirubin, total	Routine urinalysis with microscopic examination on positives(a): Color appearance, specific gravity pH protein glucose ketones occult blood

Hematology	Serum Chemistry	Urinalysis
percentage and absolute differential counts	protein, total, serum	leukocyte esterase (or equivalent)
platelet count (RBC)	gamma-glutamyl transferase ( $\gamma$ GT)	nitrite
red cell count		bilirubin
white blood cell count (WBC)	Renal function panel: Albumin, serum BUN BUN: creatinine ratio calcium, serum carbon dioxide, total chloride, serum creatinine, serum glucose, serum phosphorus, serum potassium, serum sodium, serum	urobilinogen
	Lipid panel: Cholesterol, total high-density lipoprotein (HDL) cholesterol low-density lipoprotein (LDL) cholesterol (direct) triglycerides non-HDL cholesterol (calculated) Free fatty acid (FFA)	
	Additional parameters: Lactic acid dehydrogenase (LDH) Magnesium Uric Acid	

## Other Assessments

Serum/Plasma/Whole Blood	Urine	Breath
HBsAg	Drug Screen Profile	Alcohol breath test at timepoints stated in the SOE at the investigational site
Anti-HCV	Urine drug screen via commercial kit at the investigational site.	
Anti HIV		
TSH		
PTT	Female Subjects Only	
INR	human chorionic gonadotropin (hCG)	
Glucose Metabolism Parameter:		
FPG	follicle-stimulating hormone (FSH) test for postmenopausal women (defined as amenorrheic	
Fasting Insulin		
HbA1c		

---

Malonyl carnitine  
Adiponectin, total and high  
molecular weight  
FGF21

female subjects <55 years of age  
and not surgically sterile) at  
Screening.

Biomarkers:  
Hyaluronic acid (HA)  
Procollagen III amino terminal  
peptide (PIIINP)  
Tissue inhibitor of  
metalloproteinases 1 (TIMP-1)  
Cytokeratin-18 (CK-18)  
fragments  
FibroSure (NASH)  
PRO-C3

---

(a) Microscopic analysis should be performed only if urine evaluations are abnormal.

The central laboratory will perform all necessary safety laboratory tests listed above. The results of safety laboratory tests and test to determine subjects' eligibility will be sent to the Investigator or designee, who is responsible for reviewing these results. All laboratory safety data will be faxed or transferred electronically.

Laboratory reports must be signed and dated by the Investigator or designee indicating that the report has been reviewed and any abnormalities have been assessed for clinical significance.

All clinically significant laboratory abnormalities must be recorded as an AE. A clinically significant laboratory abnormality may be verified by retesting and may be followed upon discretion of the Investigator.

### **9.1.9 Contraception**

#### **Female subjects of non-childbearing potential**

Female subjects of non-childbearing potential must meet the following criteria:

a) are either surgically sterile (hysterectomy, bilateral tubal ligation, bilateral salpingectomy, and/or bilateral oophorectomy) at least 6 months before the Screening Visit. If females' sterility is confirmed, no pregnancy testing is required during the study. The site will make an effort to retrieve medical records to document the sterility, however, the absence of records will not exclude the subject. In case that medical records cannot be obtained, serum pregnancy testing will be conducted at Screening, and urine pregnancy testing will be conducted throughout the study.

b) are post-menopausal, defined as spontaneous amenorrhea for > 12 months at the Screening Visit. Postmenopausal status will be confirmed through testing of FSH levels

outside the normal range (as specified by responsible lab) at screening for amenorrheic female subjects < 55 years of age.

Female subjects who state they are postmenopausal at the screening visit but have an FSH value that does not correspond with a postmenopausal FSH level, may have a serum hCG pregnancy test performed on a separate day. If test is negative and the subject agrees to be on a highly effective contraceptive method, subject may be enrolled in the study at the discretion of the Investigator.

c) a negative serum pregnancy test before starting study treatment.

### **Female subjects of child-bearing potential**

Female subjects of child-bearing potential must meet the following criteria:

- a) a negative serum pregnancy test before starting study treatment
- b) must agree to refrain from egg donation or harvest for 90 days after last dose of study drugs.
- c) If engaged in heterosexual intercourse must agree to use highly effective methods of contraception during intercourse, throughout the study period and for 90 days after the last dose of study drugs.

Periodic abstinence (calendar, symptothermal, postovulation methods), withdrawal (coitus interruptus), spermicides only, and lactational amenorrhoea method are not acceptable methods of contraception.

Acceptable methods of contraception under this protocol are listed below.

**Female subjects** who are considered of childbearing potential must agree to use a highly effective method of contraception, which may include:

- IUD
- Abstinence: abstinence can be used, when in line with the preferred and usual lifestyle of the subject.
- If a female subject confirms that her male partner(s) has been confirmed to be clinically sterile, this method is acceptable as the only means of contraception.
- Hormonal implants

Note: Hormonal contraceptives alone are not considered an effective method of birth control for female subjects participating in this study. Oral contraceptives can be used in combination with a male barrier method. Furthermore, female condoms in combination with male condoms is not an acceptable method.

## Childbearing Potential

For all subjects of childbearing potential, all methods of contraception, including abstinence, must be in use from the time of consent through the final study visit, and for 90 days after the last dose of study drug. Subjects who are not sexually active during the Screening Period must agree to the contraceptive requirements if they become sexually active with a partner of the opposite sex during the study and for 90 days after the last dose of study drug. Unique situations that may not fall within these specifications may be discussed with the Medical Monitor on an individual basis. Female subjects will be considered of childbearing potential after the onset of their first menstrual period.

During the study, regular serum human chorionic gonadotropin (hCG) pregnancy tests will be performed for sterilized women, when medical records are not available. In addition to a negative serum hCG pregnancy test at Screening, subjects also must have a negative urine hCG pregnancy test at outpatient visits and check-in to in-house periods.

## Male subjects

Male subjects must meet the following criteria:

- a) are required to use barrier contraception (condom plus spermicide) during intercourse from Screening through study completions and for 90 days after the last dose of study drugs.
- b) must refrain from sperm donation from Screening through at least 90 days after the last dose of study drugs.

**Male subjects** who can father a child must agree to use one highly effective method of contraception, which includes:

- Abstinence: abstinence can be used, when in line with the preferred and usual lifestyle of the subject.
- If a male subject confirms that his female partner(s) is not of childbearing potential (i.e., postmenopausal or post-surgical sterilization, as defined under child bearing potential) or is using a highly effective method of contraception, this is acceptable as the only means of contraception.

Examples of highly effective methods of contraception for male subjects' female partner(s) include:

- Hormonal contraceptives in combination with male barrier contraception
- Hormonal implants
- Intrauterine device (IUD)

Male subjects with documented infertility or surgical sterilization (performed at least six months before the first dose of study drug) are exempt from the contraception requirement.

### 9.1.10 Pregnancy

In the event a subject becomes pregnant during the study, she should be withdrawn, and the study drug should be immediately discontinued. However, the subject will be encouraged to complete the post-treatment follow-up portion of the study to the extent that study procedures do not interfere with the pregnancy.

In addition, any pregnancies in the partner of a male subject during the study or for 90 days after the last dose should also be recorded.

If the pregnancy occurs at any time during the study and the 90 days of last dose of active study medication, the pregnancy should be reported immediately to the Sponsor, using a pregnancy notification form.

Study subjects will give consent on enrollment that the Investigator will report any pregnancy during the study to the Sponsor and that they will be asked to provide information about her pregnancy, delivery, and the health of her infant until age one month. Payment for all aspects of obstetrical care, child, or related care will be the subject's responsibility.

All reported pregnancies will be followed up to final outcome, using the pregnancy and pregnancy follow-up forms. The outcome, including any premature termination, will be reported to the Sponsor. An evaluation after the birth of the child may also be conducted.

Pregnancy complications must be recorded as adverse event(s). If the infant has a congenital anomaly/birth defect this must be reported and followed up as a serious adverse event.

### 9.1.11 ECG Procedure

A standard 12-lead ECG will be recorded after 5 minutes in a supine position.

The Investigator (or designee) will interpret the ECGs by use of an electronic measurement using the following categories: within normal limits, abnormal but not clinically significant, or abnormal with clinical significance. ECGs are performed according to the SOE in section [16.1](#). The following parameters will be recorded from the subject's ECG trace as calculated by the machine algorithm: heart rate, QT interval, PR interval, QRS interval, RR interval, and QTc (corrected) using the Fridericia correction ( $QTcF = QT \div \text{cube root of the R-R interval}$  [where R-R is the duration of the entire cardiac cycle]).

When ECGs are to be collected at the same time point as a blood collection, ECGs should be collected first to avoid any artificially increased heart rates due to the blood collection.

In some cases, it may be appropriate to repeat abnormal ECGs. If a machine-read QTc value is prolonged, repeat measurements may not be necessary if the Investigator's interpretation determines that the QTc value is in the acceptable range.

### **9.1.12 Check-in Procedure**

All subjects will check in to the clinic in the morning for the In-house Periods. The following will be assessed:

1. Alcohol breath test.
2. Urine drug screen.
3. Urine pregnancy tests. (The negative result of the urine pregnancy test will allow to check-in, while the negative test result of the serum pregnancy test must be available prior to dosing on C1/D1).
4. Any use of disallowed prescription or non-prescription concomitant medications within the last 24 hours.
5. Any medical condition that could interfere with glucose metabolism, as judged by the Investigator.
6. Consumption of grapefruit (grapefruit containing food and beverages), star fruit (carambola), pomegranate, Seville orange and other food components that may interact with CYP3A4, within 24 hours prior to check-in.

Subjects who fulfill one or more of the stated criteria at check-in, will not be able to continue onto the treatment period. The treatment period will be rescheduled. Each treatment period may be rescheduled one time. After that, the subject will be excluded from the study. Replacement of subjects for all dosing periods may be permitted in order to enroll sufficient subjects into the study, only after discussion with Sponsor and Investigator.

### **9.1.13 Blood Glucose Monitoring by Fingerstick**

Blood glucose might be measured by fingerstick whenever there are signs or symptoms of hypoglycemia or hyperglycemia. A confirmation measurement of the blood glucose value may be performed by YSI.

### **9.1.14 Wash-Out Period**

The wash-out period is optional and only subjects with T2DM on combination therapy with metformin and sulfonylurea will have to undergo a wash-out period to discontinue the oral drug sulfonylurea (SU) until the end of the study. Medication with metformin monotherapy will be continued throughout the entire study on the same stable dose. Discontinuation of the SU must start at least 7 days prior to C1/D-14, the start of the deuterated water labeling period (starting wash-out at least on C1/D-21). All subjects will be instructed to monitor and document their fasting plasma glucose levels daily, using a glucometer. The subjects will be instructed on how to use the glucometer. A diary will be supplied by the study site. For further details on capturing data and documentation in the diary, please see the Operational Manual. They will be frequently (at least twice weekly)

contacted by qualified study site staff in the washout period to review their fasting plasma glucose values. If a subject has a confirmed morning fasting plasma glucose level (after 8 hours of fasting) that is  $\geq 240$  mg/dL (13.3 mmol/L) and cannot be lowered to  $< 180$  mg/dL (10.0 mmol/L) in 7 days, verified by a standard laboratory analysis (ie, YSI glucose analyzer at the site), this subject will be excluded from further participation in the study.

All subjects with T2DM will be provided with a blood glucose meter with sufficient supplies and test strips to monitor blood glucose at home during wash-out, run-in and/or outpatient periods. For further details on data capturing and documentation, please see the Operational Manual.

### **9.1.15 Standardized Meals and Dietary Counseling**

Subjects will be counseled to maintain their normal diet and exercise regimen. They will be instructed not to start any new diets, supplements, or exercise programs during the study.

During in-house period(s), subjects will receive standardized meals. The same standardized meals will be served on C1/D-1 and C4/D14 to standardize conditions prior to the C1/D1 and C4/D15 assessments. These meals will be provided up to 12 hours prior to start of scheduled fasting DNL samples on C1/D1 and C4/D15.

The standardized weight maintaining meals will be provided using estimated BMR  $\times$  activity factor of 1.5 to determine daily caloric intake. Daily calories are individualized to within 200 calories of estimated BMR  $\times$  1.5.

### **9.1.16 Pharmacokinetic Assessments and Schedule**

Blood for PK analysis of the IP will be collected at the time points indicated in the SOE in section [16.1](#) and the PK sampling schedule in section [16.2](#). One 2.0 mL sample per scheduled time point will be collected and split equally to provide plasma for primary PK measurements and plasma as a secondary back-up sample. Instructions for sample processing and shipment will be provided in the Laboratory Manual. Pre-dose sampling will be taken within 15 minutes before dosing. PK blood sampling should be performed at the nominal time(s) specified in this clinical protocol. All actual PK sample collection times will be recorded in the source documents and CRF. Explanation should be provided in the source documents and CRF for missed or mishandled samples.

Concentrations of FT-4101 in plasma will be measured using a validated liquid chromatography tandem mass spectrometry (LC-MS/MS) assay.

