## 16.2 Appendix B – PK Sampling Schedule

Study Visit Cycle (C)/ Day (D)	PK Sample Collection Time Points	
C1/D1	Pre-dose	- 15 min
C1/D1	1 hour post-dose	± 15 min
C1/D1	2 hours post-dose	± 15 min
C1/D1	4 hours post-dose	± 15 min
C1/D1	6 hours post-dose	± 15 min
C1/D15	24 hours post-dose	± 4 hours
C2/D1	Pre-dose	± 15 min
C2/D15	24 hours post-dose	± 4 hours
C3/D15	24 hours post-dose	± 4 hours
C4/D4	Pre-dose	± 15 min
C4/D8	Pre-dose	± 15 min
C4/D14	Pre-dose	± 15 min
	1 hour post-dose	± 15 min
	2 hours post-dose	± 15 min
	4 hours post-dose	± 15 min
	6 hours post-dose	± 15 min
	8 hours post-dose	± 30 min
	12 hours post-dose	± 60 min
	16 hours post-dose	± 60 min
C4/D15	24 hours post-dose	± 4 hours
	30 hours post-dose	± 4 hours

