## 9.2. APPENDIX B – PK Sampling Schedule

Study Visit Cycle(C)/ Day(D)	PK Sample Collection Time Points	
C1/D1	Pre-dose	- 15 min
C1/D1	1 hour post-dose	$\pm$ 15 min
C1/D1	2 hour post-dose	$\pm$ 15 min
C1/D1	4 hour post-dose	$\pm$ 15 min
C1/D1	6 hour post-dose	$\pm$ 15 min
C1/D15	24 hour post-dose	$\pm$ 4 hours
C2/D1	Pre-dose	$\pm$ 15 min
C2/D15	24 hour post-dose	$\pm$ 4 hours
C3/D15	24 hour post-dose	$\pm$ 4 hours
C4/D4	Pre-dose	$\pm$ 15 min
C4/D8	Pre-dose	$\pm$ 15 min
C4/D14	Pre-dose	$\pm$ 15 min
	1 hour post-dose	$\pm$ 15 min
	2 hour post-dose	$\pm$ 15 min
	4 hour post-dose	$\pm$ 15 min
	6 hour post-dose	$\pm$ 15 min
	8 hour post-dose	$\pm$ 30 min
	12 hour post-dose	$\pm$ 60 min
	16 hour post-dose	$\pm$ 60 min
C4/D15	24 hour post-dose	$\pm$ 4 hours
	30 hour post-dose	$\pm$ 4 hours

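### Both Appendix B tables give four pre-dose PK samples a ±15-minute window, which contradicts the before-dosing rule in Protocol 9.1.16, and the SAP has no rule to keep a post-dose draw out of the pre-dose summaries

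*Protocol*

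**What the plan says.** Protocol 9.1.16 sets the rule in its text, "Pre-dose sampling will be taken within 15 minutes before dosing", and in the same section refers the reader to "the PK sampling schedule in section" 16.2, which is Appendix B.

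Appendix B of the protocol has five pre-dose rows:
- "C1/D1 Pre-dose - 15 min"
- "C2/D1 Pre-dose ± 15 min"
- "C4/D4 Pre-dose ± 15 min"
- "C4/D8 Pre-dose ± 15 min"
- "C4/D14 Pre-dose ± 15 min"

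SAP 9.2 repeats the table with the same windows, including the row "C4/D14 Pre-dose", which again carries ±15 min.

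For the analysis, SAP 6.9.1 summarizes concentrations by treatment group, visit and nominal time point, lists the difference between nominal and actual sampling time, and plots all trough samples across cycles. SAP 6.9.2 derives parameters from actual elapsed time and defines Ctrough from C1D15 and later 24-hour post-dose samples.

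**The concern.** A sample labelled pre-dose is meant to hold no drug from that day's dose. A two-sided window around dosing accepts one that does. The one-sided entry at C1/D1 in both tables shows that the ± sign in the other rows is not a fault of text extraction.

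The four samples have different uses. C2/D1 is the only PK sample at the end of a week without drug. C4/D4 and C4/D8 are the pre-dose levels during Cycle 4. C4/D14 opens the full multiple-dose profile from which AUCtau is derived. With about 10 active subjects per dose, one contaminated value could shift a mean, and nothing in the SAP tells the programmer to leave it out.

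**Working it through.** **Windows compared.** Of the five pre-dose rows, one (C1/D1) matches 9.1.16 and four do not. For those four, Appendix B allows -15 to +15 min. That is 30 minutes, of which 15 (half) fall after dosing. Under 9.1.16 the latest in-window draw is at 0 min. The plan gives no figure for the effect, so there is none to reproduce.

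**Inputs for an illustration.** From Protocol 4.3: accumulation R of 1.6 to 2-fold, read here as once-daily accumulation in a one-compartment model. Assumed, because the documents give no absorption data and the first post-dose sample is at 1 h: first-order absorption ka of 0.5 to 2 per hour, no lag, and a draw at exactly +15 min. Levels are expressed relative to the initial level of a single dose, and elimination during the 15 minutes is ignored.

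1. Fraction of a level remaining after 24 h = 1 - 1/R: 0.375 (R = 1.6) or 0.5 (R = 2). Half-life = 24 × ln 2 / -ln(1 - 1/R) = about 17 h or 24 h.
2. Steady-state trough = R × (1 - 1/R) = R - 1 = 0.6 or 1.0.
3. Absorbed by 0.25 h = 1 - exp(-0.25 ka) = 0.118, 0.221 and 0.393 for ka = 0.5, 1 and 2.
4. Inflation of a steady-state pre-dose value: lowest 0.118/1.0 = 12%, highest 0.393/0.6 = 66%. If one of 10 otherwise equal values is affected, the group mean rises by 1.2 to 6.6%.

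**C2/D1.** This sample falls seven days after the C1/D15 trough. The true residual is 0.375^7 = 0.1% to 0.5^7 = 0.8% of trough. In the least unfavourable pairing (R = 2, ka = 0.5), the residual is 0.0078 and the new dose adds 0.118, so the new dose makes up 0.118/0.126 = 94% of the reading. Absorption of only 0.8% of the dose would double the true value.

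**AUCtau.** Suppose the contaminated C4/D14 value were placed at time zero. The first trapezoid (0 to 1 h) would gain at most 0.5 × 1 h × 0.66 = 0.33 trough-hours.
- If AUCtau is taken at its floor of 24 trough-hours, the error is 0.33/24 = 1.4%.
- Under the same model AUCtau is 1/k. For R = 1.6, k = 0.981/24 = 0.0409 per hour, so AUCtau = 24.5/0.6 = 40.8 trough-hours and the error is 0.33/40.8 = 0.8%.
- For R = 2, AUCtau is 34.6 trough-hours and the error is at most 0.5 × 0.393/34.6 = 0.6%.

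If the sample is instead entered at its actual time of +0.25 h, the profile has no time-zero value. SAP 6.9.2 does not impute missing concentrations and has no rule for this case. The missing quarter hour is worth at most about 0.25 × (1 + 1.66)/2 = 0.33 trough-hours, again about 0.8%.

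**Ctrough.** None of the four samples is named in the SAP definition, so there is no effect.

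**The case against.** The strongest reply is that a post-dose draw would require a site to ignore much of the protocol. Section 9.1.16 is binding text, and the rows themselves say pre-dose. Section 6.2 describes the PK samples at C2/D1, C4/D4 and C4/D8 as pre-dose and lists pre-dose and post-dose sampling at C4/D14. Footnote f to the Schedule of Events holds the dose on visit mornings in the active treatment period until fasting procedures are done. At C4/D4 and C4/D8 the DNL blood must also be taken before dosing. Actual collection times go into the source documents and CRF, and SAP 6.9.1 lists their difference from nominal. All PK output is descriptive, and no test, power figure or escalation rule depends on these samples.

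Most of this stands, and it limits the point. A reader might infer that a late draw would be neither a deviation nor visible. The documents do not support that: it would breach 9.1.16 and its time difference would appear in the listing. A reader might also infer that the secondary PK parameters are materially biased. They are not, as the Ctrough definition and the AUCtau figures show.

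Two things are left. Footnote f does not name PK sampling, and the DNL rule does not reach C2/D1 or C4/D14, where no DNL blood is drawn. And a listed time difference is not an exclusion: the summaries run on nominal time, and no sentence removes a value drawn after the dose.

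**Conclusion.** The contradiction is real and can be checked from the text alone: four of five pre-dose rows, in both tables, conflict with 9.1.16. It is a minor internal inconsistency and reads as a slip in the table, not as a decision to sample after dosing.

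The exposure is confined to the descriptive pre-dose summaries, possibly the trough plots (the SAP does not say which samples count as trough there), and the time-zero value of the C4/D14 profile. Ctrough is unaffected, and the effect on AUCtau is about 1% or less (1.4% on the crudest floor).

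The size for a single pre-dose value is not known. The 12 to 66% range rests on assumed absorption rates, no capsule lag and a draw at the last in-window minute. A lag or an earlier draw would make it smaller. It should not be read as an expected bias. The C2/D1 conclusion is less sensitive to the chosen rate, because the true off-week value is so low that any appreciable absorption would swamp it, though a lag of 15 minutes or more would remove the effect there too.

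**What to change.** In Protocol 16.2 and SAP 9.2, change the window for the C2/D1, C4/D4, C4/D8 and C4/D14 pre-dose rows from ±15 min to -15 min, to match 9.1.16 and the C1/D1 row. In SAP 6.9.1, state that any sample whose actual collection time is after that day's dose is excluded from the pre-dose summaries and the trough plots, and remains in the listing with a flag.

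The cost is four table cells in each of two documents and one SAP sentence. No visit, dose, sample count or parameter definition changes.
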